4.4 Secondary Endpoints

- Dose limiting toxicities (DLTs): For the purposes of this study, a DLT will be defined as any treatment-emergent grade 3-5 toxicity, scored using the Common Terminology Criteria for Adverse Events (CTCAE) version 4.0, and occurring within 30 days after treatment with SBRT in combination with FLT3 ligand therapy. Asymptomatic laboratory abnormalities (e.g.: leukocytosis) that do not require intervention will not be counted as DLTs. For subjects who receive more than one “cycle” of SBRT and FLT3 ligand, only adverse events that occur after the first cycle will be scored as potential DLTs.
- Clinical/radiographic endpoints: These will include radiographic response rates, disease progression, and death. Radiographic endpoints will be scored using according to immune-related response criteria (irRC).[31] To allow comparison of our data with historical experiences, we will also score radiographic findings using RECIST 1.1 criteria.[32] Pre- and post-treatment assessments will include PET/CT imaging, so that we can assess responses using PERCIST criteria[33] and with volumetric PET measures, which have been shown to be prognostic in metastatic NSCLC patients [34, 35] and predictive of clinical outcomes in advanced NSCLC patients treated with targeted therapy.[36] SBRT target lesions will not be considered in the radiographic evaluation of treatment responses, as rates of treatment response and disease control in lesions treated

with SBRT have been shown to be excellent and may not be indicative of the effectiveness of combined modality therapy.

- Potential surrogate outcomes for clinical endpoints: We will collect plasma samples at regular intervals to facilitate monitoring immune responses such as DC expansion. We will also follow T-cell inducible costimulator (ICOS) expression. ICOS is a member of the immunoglobulin superfamily. Responses to immunotherapy have been associated with increased ICOS expression on CD8+ T-cells, particularly following CTLA-4 blockade.[37-40] We will follow serum levels of high-mobility group box 1 (HMGB1), whose release has been linked to antitumor immune responses.[41, 42] Flow cytometry will be performed to track measures of DC maturation such as CD83 and CD86 expression.[43] Other correlative studies will be performed in collaboration with [name] laboratory and the study sponsor.

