6.0 STATISTICAL CONSIDERATIONS

6.1 Primary Endpoint – Progression-Free Survival

Cohort 1:

We will present the progression free survival rate at 4 months as a percentage along with its 95% confidence interval. In addition, Progression-free survival will be examined using the Kaplan-Meier method.

A total of 29 patients will be enrolled in Cohort 1 to test the null hypothesis (H0) that PFS4 is 20% or less versus the alternative hypothesis (H1) that PFS4 is 40.5% or greater. If at least 10 of 29 patients are alive without progression at 4 months, this study regimen will be considered for further development in this setting. Using this criterion, the probability of pursuing this regimen for further study if the true PFS4 is $\geq 40.5\%$ is at least 80%. The chance that this regimen will be considered for further development if the true PFS4 is 20% or lower is at most 5%.

Cohort 2:

A total of 20 patients will be enrolled in Cohort 2. We will estimate the PFS4 probability along with its 95% confidence interval using the Kaplan Meier survival procedure. We will also present median progression-free survival duration.

We assume a type-II censoring mechanism in this study, where the study will continue until 16 events occur in this cohort. We also hypothesize that progression-free survival durations will follow an exponential distribution with a mean of 5.8 months. Under these assumptions, a sample size of 20 subjects would produce a two-sided 95% confidence interval width of 4.4 months for the median progression-free survival duration (95% CI: 2.6 months to 7.0 months).

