6.2 Secondary Endpoints - Safety and Tolerability

An early stopping rule for safety will be implemented for Cohort 1 as follows. After the first 6 patients have been enrolled, accrual will be temporarily suspended while these patients are monitored for occurrence of DLTs. The trial will be terminated early if more than 1 patient experiences a DLT. If 1 or fewer grade 3 toxicities and 0 grade 5 toxicities are observed after the sixth patient has been observed for 30 days following completion of treatment, the trial will continue until a total of 29 patients have been evaluated. At the end of the trial, the treatment will be considered safe and worthy of further study if no more than 4 patients experience a DLT. For the first six patients enrolled, we will not initiate treatment for more than one patient on the same day.

The target Grade 3 toxicity rate is no more than 10% and a toxicity rate greater than 30% is considered clinically unacceptable. The design specified above has the following operating characteristics: The probability of accepting the treatment for further study if the toxicity rate is unacceptably high ($>30\%$) is at most 4%. In contrast, there is at least an 84% probability of accepting the treatment for further study if the toxicity rate is less than 10%.

The proportion of patients who develop a DLT will be computed. 95% confidence intervals for the DLT rate will be calculated using Clopper-Pearson exact confidence method.

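### The 84% acceptance probability in section 6.2 matches the final 4-of-29 rule alone; with the six-patient stop included it is 77.9% at a 10% toxicity rate.

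*Combined protocol and SAP*

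**What the plan says.** Section 6.2 gives Cohort 1 an early look and a final rule. After six patients, "accrual will be temporarily suspended while these patients are monitored for occurrence of DLTs". The early rule reads: "The trial will be terminated early if more than 1 patient experiences a DLT". If the trial goes on to 29 patients, "the treatment will be considered safe and worthy of further study if no more than 4 patients experience a DLT".

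The next paragraph names 10% as the target toxicity rate and treats anything above 30% as unacceptable. It continues: "The design specified above has the following operating characteristics". Two figures follow: at most a 4% probability of acceptance if the rate exceeds 30%, and "there is at least an 84% probability of accepting the treatment for further study if the toxicity rate is less than 10" percent. Nothing limits either figure to the final rule.

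The condition for resuming accrual is worded differently from the condition for stopping: "If 1 or fewer grade 3 toxicities and 0 grade 5 toxicities are observed after the sixth patient has been observed for 30 days". Section 4.4 supplies the definition behind the counts: "a DLT will be defined as any treatment-emergent grade 3-5 toxicity", within 30 days of treatment and leaving out asymptomatic laboratory abnormalities that need no intervention.

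**The concern.** A trial stopped at six patients never reaches the final decision, so it cannot end in acceptance. Any acceptance probability for the whole design must therefore be lower than the one for the final rule alone. A figure that matches the final rule to the nearest percent suggests that the early stop was left out of the calculation.

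What is at stake is the stated chance that a tolerable regimen is turned down. Section 7.2 says this is the first study to combine SBRT with FLT3 ligand, and section 6.2 is where an IRB, a DSMB or a later reader would look for that risk.

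There is also a smaller wording point. The stop and resume conditions are not complements. If exactly one of the six patients has a DLT and it is grade 5, the stop rule is not met (one patient) and neither is the resume rule (zero grade 5). The two rules also count different things: patients with a DLT in one, grade 3 toxicities in the other.

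**Working it through.** **Inputs, all from section 6.2.** Early look at 6 patients, stop at 2 or more with a DLT. Total 29 patients, so 23 remain after the look. Final acceptance at 4 or fewer DLT patients, counted over all 29. Reference rates 10% and 30%. The toxicity rate *p* is read as the probability that a patient has a DLT, and patients are taken as independent.

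**Step 1: reproduce the stated figures with the final rule alone.** With X ~ Bin(29, *p*):

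- P(X ≤ 4) at *p* = 0.10 is 0.8416
- P(X ≤ 4) at *p* = 0.30 is 0.0379

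These agree with at least 84% and at most 4%.

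**Step 2: the design as written.** Acceptance needs 0 or 1 DLT among the first 6 and a total of at most 4:

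P(accept) = Σ over x = 0, 1 of Bin(x; 6, *p*) × P(Y ≤ 4 − x), with Y ~ Bin(23, *p*).

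- *p* = 0.10: 0.5314 × 0.9269 + 0.3543 × 0.8073 = 0.4926 + 0.2860 = **0.7786**
- *p* = 0.30: 0.1176 × 0.1356 + 0.3025 × 0.0538 = 0.0160 + 0.0163 = **0.0322** (from unrounded terms)

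A simulation of 2,000,000 trials gave 0.7788 and 0.0323.

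**Step 3: where the bound fails.**

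| True DLT rate | Final rule alone | Whole design |
|---|---|---|
| 5% | 98.6% | 95.8% |
| 8% | 92.2% | 86.9% |
| 9% | 88.6% | 82.7% |
| 10% | 84.2% | 77.9% |
| 30% | 3.8% | 3.2% |

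Whole-design acceptance crosses 84% at *p* = 0.0870.

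**Step 4: where the loss comes from.** At *p* = 0.10 the early stop ends 1 − (0.5314 + 0.3543) = 0.1143 of trials. The difference between the two columns is 0.8416 − 0.7786 = 0.0630. So 0.0630 / 0.1143 = 55% of the stopped trials would have met the final rule had they continued. Rejection at a 10% rate is 1 − 0.7786 = 0.2214 for the whole design, against 1 − 0.8416 = 0.1584 for the final rule alone.

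**Step 5: other readings that might give 84%.**

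- Stop only at more than 2 of 6: 83.7% at 10% and 3.7% at 30%. This contradicts the written stop rule and falls just short of 84%.
- Count the limit of 4 only in the last 23 patients: 82.1% and 5.7%. This breaks the 4% limit.
- Enforce the zero-grade-5 condition: this can only leave 77.9% unchanged or lower it, so 77.9% is a ceiling.

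**The case against.** The arithmetic is not in dispute. The case against concerns weight.

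- **Nothing operational changes.** Safety is a secondary endpoint, and the sample size comes from the efficacy test in section 6.1 ("A total of 29 patients will be enrolled in Cohort 1 to test the null hypothesis"). The limit that protects patients, 4% at a 30% rate, holds with a little to spare. The error concerns rejecting an acceptable regimen too often, and the bound fails only over a narrow range of rates. All of this stands, and it limits the consequence.
- **The look has probably passed.** The caption of Figure 7 in section 2.5 refers to the first nine subjects. If the six-patient look was passed, acceptance from that point is 0.7786 / 0.8857 = 87.9% at 10% and 0.0322 / 0.4202 = 7.7% at 30%, so the 22.1% no longer describes the risk ahead. That is fair. But section 6.2 states properties of the design, and for those 77.9% is the right figure.
- **The source of the 84% is inferred.** The documents do not say how it was obtained. The final rule alone fits best, but whatever the source, the figure is wrong for the rules as written.
- **Toxicity rate could mean something else.** Section 6.2 states its target for grade 3 toxicity, while the rules count DLT patients. Treating them as one rate is the natural reading, but it is an assumption.
- **The grade 5 gap has a practical answer.** Accrual is already suspended at that point, section 10.2 sends SAE reports to the DSMB, and section 9.0 lets the DSMB decide whether the trial goes on. That stands, so the point is documentary only.

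**Conclusion.** The concern holds. For the two-rule design in section 6.2, the probability of accepting a treatment with a 10% DLT rate is 77.9%, about 6 points below the stated minimum. The statement is wrong for true rates from about 8.7% to 10% and correct below that. The companion figure of at most 4% is correct. The result assumes one DLT probability shared by independent patients, a final count over all 29, and a trial held for a grade 5 event treated as resumed. This is a misstated operating characteristic of a secondary safety rule: worth correcting, with no effect on the primary analysis. The grade 5 wording is a minor clarification and does not bear on this conclusion.

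**What to change.** Change one sentence in section 6.2, in either of two ways:

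1. Restate for the whole design: *With the six-patient stop and the final rule together, the probability of accepting the treatment is about 78% if the true DLT rate is 10% and about 3% if it is 30%.*
2. Keep 84% and 4%, and label them as properties of the final 4-of-29 rule only.

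Do not raise the final limit to recover 84%. Allowing 5 of 29 with the same early stop gives 84.8% at a 10% rate but 7.3% at 30%, which breaks the 4% limit.

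In the same edit, make the stop and resume conditions exhaustive and count the same thing in both: *Terminate if 2 or more of the first 6 patients have a DLT. Resume if no more than 1 has a DLT and none is grade 5. If exactly 1 has a DLT and it is grade 5, accrual stays suspended pending a DSMB decision.* If the look is already complete, this second change is for the record only.

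The cost is one corrected sentence and one clarified sentence. Boundaries, sample size, patients and procedures stay as they are.

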6.3 Other Secondary Endpoints

irRC, RECIST, and PERCIST response rates, based on first post-treatment imaging, will be reported using descriptive statistics. Rates of disease-free and overall survival will be reported using actuarial methods. Exploratory analyses will be

performed to evaluate surrogate endpoints, including radiographic responses and immune correlates, as predictors of clinical outcomes. We will also perform statistical tests to explore if response rates, time-to-event outcomes, and immune responses correlate with SBRT fraction size.

7.0 REGULATORY CONSIDERATIONS

7.1 Protection of Human Subjects

The Investigator must ensure that patients or their legally acceptable representatives are clearly and fully informed about the purpose, potential risks and other critical issues regarding clinical trials in which they volunteer to participate. Preparation of the consent form is the responsibility of the Investigator and must include all elements required by CFR 21 Part 50.25 and the local IRB.

7.2 Potential Risks

Subjects participating in this Phase II study are at risk for the development of treatment-related toxicities. Risks from lung SBRT include damage to the lungs, heart, and esophagus that may cause transient symptoms or permanent dysfunction. Risks from SBRT to other sites include damage to nearby organs, depending on the target location. The risk profile of SBRT to the lung or other sites has been characterized clearly over the past decade, and SBRT planning and dosing for patients enrolled on this study will be optimized to keep the expected risk of severe complications related to SBRT below 5%.

CDX-301 and AMG949 were generally well-tolerated in prior clinical trials. In the Celldex-sponsored phase 1 study in 30 healthy volunteers, treatment-related toxicity was infrequent and reported only at the 25 and 75 µg/kg/day dose levels. One Grade 3 event, community acquired pneumonia, was considered to be treatment-related. No additional infections, DLT, SAE, or Grade 3 toxicities were reported. All other treatment-related adverse events were Grade 1; these included lymphadenopathy in six subjects and single cases of diarrhea, injection site erythema, folliculitis, and dry mouth.

In studies of AMG949 administered as single agent to healthy volunteers (n=36), there were no deaths, SAEs, Grade 3/4 adverse events, or premature withdrawals from treatment. Grade 2 events were limited to injection site reactions and/or pain. Laboratory results were generally unremarkable and showed no suggestion of a dose response. The expected pharmacologic effects of rhuFlt3L (increased WBC and monocytes) were observed in both studies.

Across all previous trials of AMG949, the most common treatment-related adverse events were injection site reactions. These events were generally mild to moderate, consisting of erythema, induration, urticaria, pain, and bruising. Rarely, more severe reactions with blistering have also been reported. In Immunex-sponsored

studies, additional adverse events occurring for subjects receiving AMG949 with or without GM-CSF, regardless of causality, included headache, pain, asthenia, myalgia, nausea, diarrhea, arthralgia, fever, rash, paresthesia, pruritus and vomiting. The majority of adverse events were mild to moderate in severity. Serious adverse events deemed to be related to AMG949 occurred in 6 of the 294 subjects treated in Immunex-sponsored trials. These events were three cases of hypercoagulability (IV line clotting), single cases of left arm thrombosis and deep vein thrombosis in the leg, and a case of fever, chills, and hypotension.

This will be the first study combining SBRT and FLT3L therapy, so the full range of potential toxicities remains unknown.

7.3 Additional Warnings and Precautions

Drug-drug Interactions

Interactions between CDX-301 and other drugs have not been fully evaluated.

Allergic Reaction

CDX-301 is a fully human protein and it is unlikely that it will induce a hypersensitivity reaction. No such reactions have been observed in the AMG949 or CDX-301 programs to date. If such reactions were to be observed, possible manifestations could include fever, chills, rash, rigors, pruritus, or other symptoms.

Immunogenicity

None of the 30 healthy volunteers treated with CDX-301 (5 to 10-day regimen) have developed anti-rhuFlt3L antibody. Approximately 16% of subjects treated with AMG949 in Immunex sponsored studies and tested for immune response were noted to develop anti-rhuFlt3L antibody. Anti-rhuFlt3L antibodies appeared to develop more frequently in studies with greater exposure to AMG949. However, none of the anti-rhuFlt3L antibodies were neutralizing.

Coagulation

No thrombotic events have been reported as potentially related to CDX-301 in the prior healthy volunteer study. However, thrombotic events (hypercoagulability, IV line thrombosis, and venous thrombosis) were observed rarely in oncology patients (n=6) receiving AMG949 and was more common when combined with GM-CSF or G-CSF. Low grade thrombocytopenia has also been observed following AMG949 administration.

Evaluation of coagulation parameters and clotting factors in several of these patients did not reveal any abnormalities.

Autoimmune Disease

Subjects with a known history of autoimmune disorders should not be given CDX-301 until further studies have determined the safety profile of CDX-301 in this patient population. Pre-clinical studies have demonstrated that rhuFlt3L may have a complicated role in regulating autoimmune diseases and can either exacerbate or ameliorate autoimmune disease manifestations. Therefore, CDX-301 may have the potential to exacerbate autoimmune disorders by its immunomodulatory effects. Subjects administered CDX-301 will be monitored for the development of potential autoimmune phenomena, which may include asymptomatic autoantibody seroconversion or hyper- or hypothyroidism.

Development of Immune Tolerance

CDX-301-mediated increases in immature dendritic cells and/or Treg cells could potentially be tolerogenic. Therefore, CDX-301 could potentially have deleterious effects in an infectious disease setting or other pre-existing or developing disease. AMG949 worsened the outcome in a mouse *Streptococcus pneumoniae* pneumonia challenge model[44], indicating that rhuFlt3L treatment could pose a risk for increased lung injury associated with *S pneumoniae* pneumonia. Study subjects will be monitored closely for the development of infections signs and symptoms. As described in Section **Error! Reference source not found.**, any SAE will be reported to the medical monitor within 24 hours.

rhuFlt3L may also be associated with a differential response to vaccines. In another murine model, intramuscular injection of rhuFlt3L in combination with a hepatitis B vaccine suppressed the antibody response to the vaccine in a dose-dependent manner, although in situ delivery by plasmid increased the antibody response [45]. In a clinical study in which healthy volunteers were administered hepatitis B vaccine and either placebo or AMG949, there was no inter-group difference in hepatitis B antibody responses, demonstrating that AMG949 neither augmented nor tolerized humoral responses to the vaccine. Patients on this study should not receive any vaccinations until at least 28 days after the last dose of CDX-301.

Leukemia

There are data showing that prophylactic treatment with rhuFlt3L can prevent or abrogate leukemic activity[46]. There also are data showing the expression of Flt3 and the Flt3L receptor on some leukemias and extensive data that support an association between an increase in proliferation or suppression of apoptosis in clinical leukemias that

bear constitutively activated Flt3 mutations. These mutations do not appear to be causal for AML[47-50]. It is not known whether the addition of rhuFlt3L to patients with leukemia expressing Flt3 will promote leukemic proliferation or whether the ligand can promote the development of leukemia in people without pre-existing leukemia. Since the effect of administered rhuFlt3L is transient, it would seem unlikely to have any persistent effects, and no cases of leukemia were reported after rhuFlt3L administration in previous studies.

Pregnancy, Carcinogenesis, and Teratogenicity

The effects of CDX-301 on fertility, pregnancy, or the unborn fetus have not been determined. It is not known if CDX-301 is excreted in milk or can cross the placenta. For this reason, pregnant and nursing women will not be enrolled into this study. Women of childbearing potential enrolled into the clinical study must take adequate contraceptive measures.

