4.2 Study Calendar

	Pre-rx	Week 1	Week 2	Week 3	Week 4	Week 5	Week 6	Week 7	Week 8	Weeks 16, 24, 32
Stereotactic Radiotherapy (SBRT)		X X X								
FLT3 Ligand Therapy		XXXXX								
History and Physical Examination	X	X	X	X	X		X		X	X
Blood Tests: CBC, CMP	X	X	X	X	X		X		X	X
PET/CT	X								X	X
Immune Correlates	X		X		X				X	X

Additional cycles of SBRT and FLT3 ligand may be administered after 8 weeks or more in cases where treatment is well-tolerated and seems to provide clinical benefit, at the discretion of the treating physicians. In addition to the time points specified above, blood samples for immune correlates will also be drawn at the first clinic visit following disease progression. Immune correlates will include anti-drug antibody testing for CDX-301, which will be performed by sending study samples to Celldex. For diseases where PET/CT is not commonly used (e.g., hepatocellular carcinoma), PET/CT may be replaced by CT and/or MRI.

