5.0 STUDY THERAPY

5.1 Stereotactic Body Radiotherapy

- SBRT will be administered during the first week of study therapy.
- A single pulmonary or extrapulmonary lesion that measures at least 1 cm in greatest dimension will be treated.
- The target lesion for SBRT will be chosen by the treating radiation oncologist with the following considerations:
 - Confidence that the target lesion is cancerous (based on prior biopsy, growth on serial imaging, and/or hypermetabolic uptake on FDG-PET)
 - Safety of SBRT to the target lesion and ability to meet the dosimetric constraints listed below
- Based on lesion size and location, one of three SBRT schedules will be selected for each patient receiving SBRT to a pulmonary lesion. At least 95% of the planning target volume (PTV) will receive the full prescription dose. Based on the criteria described below, we expect that approximately equal numbers of subjects will receive each of these SBRT schedules:

Schedule	Criteria	Interval between treatments	Course duration
34 Gy x 1	Peripheral tumor measuring \leq 2 cm in greatest dimension and $>$ 1 cm from the chest wall	-	-
18 Gy x 3	Peripheral tumor measuring \leq 5 cm and not eligible for 34 Gy x 1 fraction	42-54 hours	5 days
10 Gy x 5	Central or peripheral tumor not eligible for 34 Gy x 1 fraction or 18 Gy x 3 fractions	18-30 hours	5 days

- Based on lesion location, the following SBRT schedules will be employed for each patient receiving SBRT to an extrapulmonary lesion. At least 95% of the planning target volume (PTV) will receive the full prescription dose. If this cannot be achieved while respecting normal tissue constraints, the prescription dose may be lowered by up to 20%. These treatment schedules are adopted from an ongoing cooperative group clinic trial (NRG-BR001):

Schedule	Target Lesion Location	Interval between treatments	Course duration
10 Gy x 3	Spinal or Paraspinal	42-54 hours	5 days
10 Gy x 3	Osseous	42-54 hours	5 days
10 Gy x 5	Mediastinal or Cervical Lymph Node	18-30 hours	5 days
15 Gy x 3	Liver	42-54 hours	5 days
15 Gy x 3	Abdominal or Pelvic (lymph node or adrenal gland)	42-54 hours	5 days

- The following normal tissue constraints will be used for SBRT planning:

	1 Fraction	3 Fractions	5 Fractions
Brachial plexus	max dose < 17.5 Gy	max dose < 21 Gy	max dose < 30 Gy
Esophagus	max dose < 15.4 Gy	max dose < 30 Gy	max dose < 32.5 Gy
Great vessels	max dose < 37 Gy	max dose < 39 Gy	max dose < 55 Gy

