5.2 FLT3 Ligand Therapy (CDX-301)

- Daily subcutaneous injections of CDX-301 (75 µg/kg) will be administered for 5 days, beginning on the first day of SBRT.
- Additional “cycles” of SBRT (to distinct lesions) and CDX-301 may be administered every 2-4 months to subjects who demonstrate evidence of clinical benefit (lack of treatment-related toxicity and no disease progression).
- Study therapy will be discontinued in cases of treatment-related toxicity or disease progression.

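### Repeat CDX-301/SBRT cycles are allowed months after entry with no repeat pregnancy test; the autoimmune monitoring statement in 7.3 also has no matching test, a secondary wording matter

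*Combined protocol and SAP*

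**What the plan says.** Pregnancy. Section 3.2 excludes women of childbearing potential with a positive serum pregnancy test. That bullet carries no time window; the 10-day window in 3.2 introduces the blood count and renal criteria and refers to the first dose of study drug. Section 7.3 says the effects of CDX-301 on pregnancy and the fetus are unknown, bars pregnant and nursing women from enrolling for that reason, and requires contraception.

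Repeat treatment. Section 4.2: "Additional cycles of SBRT and FLT3 ligand may be administered after 8 weeks or more in cases where treatment is well-tolerated", if it also seems beneficial and the treating physicians agree. Section 5.2 says further cycles "may be administered every 2-4 months to subjects who demonstrate evidence of clinical benefit (lack of treatment-related toxicity and no disease progression", and that each repeat irradiates a different lesion. The target sites in 5.1 include "Abdominal or Pelvic (lymph node or adrenal gland".

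Autoimmune monitoring. Section 7.3: "Subjects administered CDX-301 will be monitored for the development of potential autoimmune phenomena, which may include asymptomatic autoantibody seroconversion or hyper- or hypothyroidism". The calendar's safety bloods are "Blood Tests: CBC, CMP". On antibodies, 4.2 says "Immune correlates will include anti-drug antibody testing for CDX-301". Section 4.4 names dendritic cell expansion, ICOS, HMGB1 and CD83/CD86, then leaves the list open: "Other correlative studies will be performed in collaboration with" a named laboratory and the sponsor.

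**The concern.** The reason given in 7.3 for keeping pregnant women out applies equally to a second cycle two or more months later. At entry the protocol tests as well as requiring contraception; before a repeat cycle it relies on contraception alone. Each repeat brings both an agent of unknown fetal effect and high-dose radiation to a new site, which may be abdominal or pelvic even if the first target was in the chest. What is at stake is avoidable fetal exposure in a patient who follows the protocol exactly.

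The autoimmune statement raises a smaller question. It gives seroconversion without symptoms as an example of what monitoring may find, but the protocol names no test that would show it.

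**Working it through.** The plan gives no figure on this point, so there is none to reproduce. The check is a comparison of sections, followed by a bound on size.

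**1. Where a pregnancy safeguard appears**

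| Section | Content | Applies to repeat cycles? |
|---|---|---|
| 3.2 | Serum test, entry exclusion, no window of its own | No |
| 4.2 calendar | No pregnancy-test row | No |
| 4.2 text, 5.2 | Conditions for repeating: tolerance, benefit, no related toxicity, no progression, physician discretion | Pregnancy not mentioned |
| 5.3, 5.4 | Modifications and toxicity management | Pregnancy not mentioned |
| 7.3 | Contraception required | Yes, but it detects nothing |

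Pregnancy tests specified before a repeat cycle: 0.

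**2. How many repeat courses**

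Inputs: 29 and 20 patients (4.1); Cohort 1 PFS4 of 20% (null) or 40.5% (alternative), with PFS4 read at 16 weeks (4.3, 6.1); Cohort 2 exponential with mean 5.8 months (6.1). Assumptions: Cohort 1 is also exponential, there is one repeat at 2 months, and every progression-free patient is re-treated. With 30.4375 days per month, 2 months is 60.875 days, or 8.70 weeks.

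- Cohort 1, progression-free = 29 × PFS4^(8.70/16): 29 × 0.20^0.5435 = 12.1; 29 × 0.405^0.5435 = 17.7.
- Cohort 2, progression-free = 20 × exp(−2/5.8) = 14.2.
- Total: 12.1 + 14.2 = 26.3 to 17.7 + 14.2 = 31.9, so about 26-32 courses in both sexes. At an assumed 50% uptake, about 13-16.
- Women, using the 24 of 49 projected in 7.6: 26.3 × 24/49 = 12.9 to 31.9 × 24/49 = 15.6 at full uptake.
- The share of childbearing potential is not given. At an assumed 10%, about 1.3-1.6 re-exposures without a specified test at full uptake (0.6-0.8 at 50% uptake); at an assumed 50%, about 6.4-7.8 at full uptake.

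These are re-exposures, not pregnancies. The documents support no pregnancy rate.

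**3. Whether scheduled draws can carry the test**

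With repeats at 2, 4 and 6 months, the gap from the nearest preceding draw is:

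- week 8: 60.875 − 56 = 4.9 days;
- week 16: 121.75 − 112 = 9.8 days;
- week 24: 182.625 − 168 = 14.6 days.

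Only the first falls within 7 days. Later repeats need a test at SBRT planning or on day 1.

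**4. Autoimmune statement against the schedule**

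CBC and CMP are drawn at 10 time points (pre-treatment and weeks 1, 2, 3, 4, 6, 8, 16, 24, 32). Neither is a thyroid or autoantibody test. The anti-drug antibody assay measures antibody to CDX-301, not to self. The open clause in 4.4 does not rule out such an assay but names none. History, examination and adverse event recording (10.0) cover symptomatic disease, including clinical thyroid disease, but do not test for seroconversion without symptoms.

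**The case against.** On pregnancy, the other side can say that contraception is mandatory, that few women will be affected, and that clinicians commonly test before radiotherapy. The first two reduce the risk. The third is not in the protocol. None answers why a test is needed at entry but not before a repeat. The consent pages were not available to this review and may say more, but the conditions for re-treatment are in 4.2 and 5.2, which are silent.

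On size, a reader might infer far more exposure. Repeats every 2 months in every progression-free patient would give about 51-67 courses by week 32. The documents do not support that as an expectation. Section 5.2 requires a distinct lesion each time, while 3.1 guarantees only one lesion suitable for SBRT; the second need only be measurable and outside the fields. Three repeats would need four treatable lesions.

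On autoimmunity, a reader might infer that a safety commitment is being broken. The objection to that largely stands. The wording of 7.3 lists phenomena that might arise and does not promise assays. Section 3.2 excludes a history of autoimmune disease, and the concern in 7.3 is pre-clinical. Section 7.2 lists no autoimmune or thyroid event in 30 CDX-301 or 36 AMG949 volunteers, or among 6 related serious events in 294 subjects.

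A broad autoantibody screen could also do harm. Section 5.2 stops therapy for treatment-related toxicity with no grade threshold, so a titre without symptoms could end treatment in a patient who is benefiting. Since repeats may begin at week 8, this could happen before the week-16 endpoint. Prior PD-1/PD-L1 therapy, required in Cohort 2, would complicate attribution.

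**Conclusion.** The pregnancy gap is real and worth closing: one entry test, no re-test, and repeat cycles permitted months later with an agent of unknown fetal effect plus radiation. The number of women concerned cannot be derived from the documents. At the planning values, one repeat at about 2 months gives at most about 26-32 courses across both sexes. This rests on an exponential shape in Cohort 1 and full uptake; toxicity, physician discretion and the distinct-lesion rule would lower it, while PFS4 above 40.5% or further repeats would raise it. The gap itself does not depend on the count.

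The autoimmune part is secondary: a mismatch between 7.3 and the schedule that either a test or a wording change can resolve. A reader might infer that autoimmune toxicity goes unmonitored or that the trial's results are compromised. Neither follows. Symptomatic disease is covered, and for the DLT count 4.4 already says "Asymptomatic laboratory abnormalities (e.g.: leukocytosis) that do not require intervention will not be counted as DLTs". PFS4, alpha and power are unaffected by the gap.

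**What to change.** In 4.2 and 5.2, require a negative serum pregnancy test in women of childbearing potential before every cycle, including the first, within 7 days of that cycle's first CDX-301 dose or SBRT fraction. Where the scheduled draw falls outside the window, take the sample at the SBRT planning visit or on day 1, with the result known before treatment. Add a row to the calendar. The cost is one extra blood test per cycle in a small number of women, plus amendment wording; sample size and analysis do not change.

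Optionally, settle 7.3 in one of two ways:

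- **Add TSH** at baseline and on existing draws, and state that an asymptomatic abnormality needing no intervention does not by itself stop therapy under 5.2. Each time point costs up to 49 tests; baseline, week 8 and week 16 would be 3 × 49 = 147 if all patients reach week 16. TSH does not detect seroconversion, so that example should then be dropped from 7.3.
- **Narrow 7.3** to the history, examination and adverse event recording actually done. This needs no assays.
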